7.3.1. Selection and Timing of Doses

Not applicable.

7.4. Blinding

This is an open-label pragmatic study. As with most behavioral interventions, it will not be possible to fully blind researchers, healthcare providers, and study patients to intervention vs. usual care assignments. However, we have purposefully designed our trial to prevent certain threats to contamination between study arms. Patients will be told they will receive one of two models of care. While they will not be deliberately made aware of the approach not received, we do recognize that there is an unavoidable risk of patients learning from other patients involved in the study.

7.5. Dosage Modification

Not applicable.

7.6. Preparation/Handling/Storage/Accountability

Not applicable.

7.7. Treatment Compliance

Patient compliance with intervention will be assessed at end of intervention course. Compliance will be assessed during patient interviews.

7.8. Concomitant Therapy

Not applicable.

7.9. Treatment after the End of the Study

7.9.1. Study Extensions [if applicable]

Not applicable.

7.9.2. Continued Access

Not applicable.

7.9.3. Special Treatment Considerations [if applicable]

Not applicable.

7.9.4. Patient Follow-Up in Pragmatic Trials [if applicable]

The T2 interview will take place over the phone 3 months after T1. Patients in the EMC² strategy group will also receive portal questionnaires.

8. Discontinuation Criteria

8.1. Discontinuation from Pragmatic Study Treatment

8.1.1. Permanent Discontinuation from Study Treatment

There are no anticipated circumstances when a patient would be withdrawn from the study without their consent, unless they pose a threat to themselves or research staff.

Patients can choose to withdraw from the study at any time. If a patient chooses to withdraw from the research, any data collected up until the point of withdrawal will still be utilized, as it will not include identifying information.

8.1.2. Temporary Discontinuation from Study Treatment Not applicable.

8.1.3. Discontinuation of Inadvertently Enrolled Patients

If the sponsor or investigator identify a patient who did not meet enrollment criteria and was inadvertently enrolled, a discussion must occur between the sponsor and the investigator to determine if the patient may continue in the study. If both agree it is appropriate to continue, documented approval from the sponsor will be obtained to allow the inadvertently enrolled patient to continue in the study.

Some possible reasons that may lead to permanent discontinuation include:

- participation in the study needs to be stopped for medical, safety, regulatory, or other reasons consistent with applicable laws, regulations, and good clinical practice (GCP)
- investigator decision
 - o the investigator decides that the patient should be discontinued from the study
- patient decision
 - the patient or the patient's designee, for example, parents or legal guardian requests to be withdrawn from the study

8.2. Lost to Follow-Up

A patient will be considered lost to follow-up if he or she repeatedly fails to return for scheduled visits and is unable to be contacted by the study site. Site personnel are expected to make diligent attempts to contact patients who fail to return for a scheduled visit or were otherwise unable to be followed up by the site.

9. Pragmatic Study Assessments and Procedures

Please see section 5 for the Schedule of Activities, with the study procedures and their timing.

9.1. Effectiveness Assessments

9.1.1. Primary Effectiveness Assessments

Medication Knowledge. Medication-specific knowledge measures will be created to determine whether a patient has a basic understanding of their prescribed medication. This will comprise a set of objective, open-ended, yet targeted questions with predetermined correct responses known for each medication under study. Patients will be asked about their medication's 1) indication, 2) risks or warnings (knowledge of at risk/warnings, correct or incorrect per warning), and 3) side effects (knowledge of at least two side effects, correct or incorrect per item). Correct answers will be tailored to the available content included in the MedGuide Summary, as done previously by our team.(11-14) While patients are not given response options to facilitate their answer, interviewers will both document the verbatim response to each question and code it as correct or incorrect. A second, independent reviewer, blinded to the research interviewer's code of correct/incorrect, will rate the responses. Any discordance will be resolved through team discussions. Total scores will range from 0-100, calculated reflecting the percent correct of possible points.

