Title of Study:

Development and Evaluation of an Electronic health Record-based Medication Complete Communication (EMC²) Strategy: A Pragmatic, Physician Randomized Trial

Rationale:

There is a well-documented need for effective interventions that can help patients understand and safely adhere to prescribed medications, particularly those with greater potential for harm if not taken correctly. We will leverage health and consumer technologies with our **EHR-based Medication Complete Communication (EMC²) Strategy** to: 1) inform patients about medication risks and safe use, 2) promote provider education and counseling about prescribed drugs and 3) monitor patient adherence outside of visits. The EMC² Strategy could be feasible, sustainable, and readily available to ambulatory care practices.

Objective(s)/Endpoints:

Objectives	Endpoints
Primary • Test the effectiveness of the EMC ² Strategy, compared to usual care on improvement in patient knowledge of prescribed medications	Medication-specific knowledge measured by demonstrated proper understanding of indication, risks and benefits, and side effects at 3 months.
Secondary • Test the effectiveness of the EMC ² Strategy, compared to usual care on improvement in safe use and adherence to prescribed medications	Medication adherence measured by fill, time to fill, demonstrated proper use, and the ASK-12. at 3 months
Tertiary/Exploratory • Evaluate the fidelity of the EMC ² Strategy	 Patient report of provider counseling Patient report of receipt of print Rx information Completion of EHR portal survey Clinic follow-up (yes or no) for patients identifying Rx concerns via portal survey

Summary of Pragmatic Study Design:

Study B3D-US-B029 (STU00207507) is a 2-arm, multi-site, physician-randomized pragmatic trial to evaluate the impact and scalability of the Phase I EMC^2 strategy to promote safe medication use and adherence.

Treatment Arms and Duration:

Usual Care. Usual care includes 1) variable provider counseling with limited or variable EHR notifications or counseling support; 2) no distribution of print medication information materials, including FDA Medication Guides in clinics and variable distribution in pharmacies; and 3) limited or no active surveillance of medication use postvisits.

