7.1. Treatments Administered

This pragmatic study involves a comparison of intervention administered with standard of care in routine care.

Study Arms.

Usual Care: For this study, current usual care includes 1) variable provider counseling without any EHR notifications or counseling support; 2) variable distribution of print medication information materials, including FDA Medication Guides in clinics and variable distribution in pharmacies; and 3) limited or variable active surveillance of medication use post-visits.

Intervention: EMC² Strategy: There are several components that will be embedded into the workflow via EHR/patient portal platforms, mostly automating their implementation. Following patient movement through a provider visit, the following 6 activities will occur:

- 1. *Physician Medication Alert:* If a prescribing physician attempts to place a new order or change to an existing study medication prescription, an EHR-generated alert will notify the provider that the medication requires patient counseling. Physicians can opt to ignore this alert.
- 2. *Provider Counseling Support:* Content from the 1-page, Med Guide Summary will appear on the screen, if selected by the provider, to orient and inform provider-patient discussion.
- 3. Automated Delivery of Med Guide + Summary: When patients leave an encounter, the medication order in Epic will automatically cue printing of both the 1-page, health literate Med Guide Summary for study medications and a full Med Guide, if applicable (latter is required by FDA for certain medications only, the former designed to enhance comprehension). If the medication was ordered during a telemedicine encounter, the Med Guide Summary will automatically populate in the patient portal.
- 4. Follow-Up Portal Questionnaire: Within 1 week post-visit, patients will receive an automated email prompting them to log on to the patient portal. Patients' will be asked to fill out a short set of questions related to medication adherence, and other medication-related concerns (i.e. cost, side effects). If patients have not completed the questionnaire within 2 days, another email reminder will be sent. The information submitted back by the patient will be stored in the EHR.

Content in question form and corresponding responses for the portal questionnaire will be revised from prior evaluation scripts and written by Drs. [name], [name], [name], and [name].

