For More Information	It is important to read all the additional information about your medicine you get from your pharmacy. If you have questions, ask your doctor or pharmacist. You can find more helpful information at www.nlm.nih.qov/medlineplus

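### The primary knowledge score is keyed to a sheet that the plan gives only to the EMC² arm, so the arm difference can be inflated if usual-care patients give more true answers that the sheet omits

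*Combined protocol and SAP*

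**What the plan says.** Section 9.1.1 builds the primary outcome from "open-ended, yet targeted questions with predetermined correct responses known for each medication under study", covering indication, risks or warnings, and side effects. On the content of the key it says: "Correct answers will be tailored to the available content included in the MedGuide Summary". On the scale: "Total scores will range from 0-100, calculated reflecting the percent correct of possible points". Interviewers write down each answer verbatim and code it. On the second rating: "A second, independent reviewer, blinded to the research interviewer's code of correct/incorrect, will rate the responses". Disagreements go to team discussion. The section does not say how an answer that is true of the drug but absent from the Summary is coded, or whether either rater is masked to arm. Section 7.4 accepts that "it will not be possible to fully blind researchers, healthcare providers, and study patients to intervention vs. usual care assignments".

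The Summary belongs to the intervention. Under section 7.1, item 3, "the medication order in Epic will automatically cue printing of both the 1-page, health literate Med Guide Summary for study medications", and after a telemedicine encounter it appears in the portal. Item 2 lets the prescriber bring its content up on screen to guide counselling. Under section 10.3.3.3 only intervention patients are asked whether they received it.

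The Synopsis describes usual care as "no distribution of print medication information materials, including FDA Medication Guides in clinics and variable distribution in pharmacies", whereas section 7.1 calls clinic distribution of print material variable. The two should be reconciled, but neither gives the Summary to usual-care patients. Section 10.3.3.1 analyses the score under this single key and plans no analysis under another.

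**The concern.** The objective is better patient knowledge of the prescribed medicine than under usual care. A key drawn from one arm's teaching material measures that knowledge fairly only if patients in both arms are equally likely to phrase what they know in terms the key recognises. EMC² patients are handed the key's content and may hear it from a prescriber who has it on screen. Usual-care patients learn from labels, leaflets, pharmacists and prescribers. The example sheet in Attachment 3 does not present itself as complete, since it tells the patient: "It is important to read all the additional information about your medicine you get from your pharmacy".

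If true answers outside the Summary go uncredited and are more common in usual care, part of the measured effect on the only primary endpoint is recall of the sheet. The second rating works from the same key, so it would not remove this. No planned analysis would show whether it happened.

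**Working it through.** **1. The plan's own figure.** Inputs from section 10.1: SD 28.4, 150 evaluable patients per arm, 6 per provider, ICC 0.001, 80% power, expected usual-care mean 55.6%. Two-sided alpha 0.05 is from section 10.3.1.

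- Design effect = 1 + (6 − 1) × 0.001 = 1.005.
- Standard error of the difference = 28.4 × √(2 × 1.005 / 150) = 3.29 points.
- Providers = 300 / 6 = 50, so 50 − 2 = 48 degrees of freedom.
- Minimum detectable difference from the noncentral t with 48 df = 9.40 points, matching the stated 9.4. With ICC 0.01 the same method gives 9.61, matching the stated 9.6.

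The sample-size figure is therefore sound and serves as the yardstick below.

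**2. What the key does to the difference.** Let K be true knowledge on the 0-100 scale and q the share of true answers that fall outside the Summary and are not credited. The observed score is K × (1 − q) in each arm. If K is equal in both arms, the observed difference (EMC² minus usual care) is K × (q in usual care − q in EMC²) = K × x, where x is the excess off-key share in usual care.

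**3. Size under no true difference.** The documents give no value for x, so this is a range and not an estimate. Assumption: K = 55.6 in both arms. The chance of a significant result uses a noncentral t with 48 df, noncentrality 55.6x / 3.29, and ICC 0.001.

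| Excess x | False difference, 55.6 × x | Chance of p < 0.05 with no true difference |
|---|---|---|
| 0 | 0 | 5.0% |
| 2% | 1.1 points | 6.3% |
| 5% | 2.8 points | 13.2% |
| 10% | 5.6 points | 38.1% |
| 16.9% | 9.4 points | 80.0% |

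The last row is the excess that would produce the whole target difference by itself: 9.4 / 55.6 = 0.169. Here x is a share of all true answers on scored items, indication included. If the excess arises only on warnings and side effects, x over the whole score is correspondingly smaller.

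**4. Equal shares.** If q is the same in both arms, no false difference arises and a true one shrinks by the factor 1 − q. A true 9.4 becomes 9.4 × 0.95 = 8.9, 9.4 × 0.90 = 8.5 or 9.4 × 0.80 = 7.5 points for q of 5%, 10% or 20%.

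**The case against.** The strongest reply is that one key applies to both arms, and that scoring a few chosen messages is a legitimate way to define basic understanding, which is what section 9.1.1 sets out to measure. An answer that matches the Summary scores as correct wherever the patient learned it. The example sheet in Attachment 3 is broad: purpose, benefit, warnings, four common side effects, and low blood sugar, low potassium and allergy with their signs. Ordinary knowledge of that drug would often match it. EMC² patients also receive the full Med Guide where applicable, and more counselling, so they too can give true answers outside the Summary. If extra answers are allowed, a patient who names two listed side effects and one unlisted may lose nothing. Section 9.1.1 also cites earlier use of the method by the same team. Those reports are not available here, so the precedent can be neither relied on nor dismissed.

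Much of this stands, and it rules out some stronger readings. A reader might infer that true off-Summary answers are coded incorrect. That is a natural reading of a predetermined key, but section 9.1.1 does not say so. A reader might also infer that the bias is present and always favours EMC². That needs a higher off-key share in usual care, which is plausible because only one arm is shown the key, but which the documents neither state nor quantify.

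What does not stand is that an identical key settles the matter. Exposure to the key differs by design, the rule for off-Summary answers is unwritten, and masking of raters to arm is not stated.

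**Conclusion.** The primary score is aligned with material that the documents assign only to the EMC² arm, so the arm difference can be inflated. The documents do not show that it is. Each 1% of excess off-key share in usual care adds about 0.56 points of false difference, assuming true knowledge of 55.6% in both arms and no credit for off-Summary answers. Excesses of 5% and 10% give about 2.8 and 5.6 points against the 9.4 points the trial is sized for. If the Summary and other drug information overlap almost fully, or the off-key shares are equal, the false difference is close to zero. As planned, the analysis could not tell these cases apart, and a positive result could not separate knowledge of the medicine from recall of the sheet. The sample-size calculation is not in question.

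**What to change.** In section 9.1.1, before T2 coding starts, state that a response is scored correct if it is true under the drug's approved labelling (the Med Guide where one exists, otherwise the prescribing information), whether or not it is on the Summary. Fix the answer list for each drug in advance, and report the Summary-keyed score alongside so that the gap between the two is visible.

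If the sponsor prefers to keep the Summary key as primary, the minimum is to state how true off-Summary answers are coded and to pre-specify a labelling-keyed re-scoring of the verbatim responses as a sensitivity analysis of the primary outcome. Under either option, coding should be done without sight of arm where existing staff allow. The second reviewer, for example, could work from the verbatim text alone.

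No new data are needed, because verbatim answers are already recorded. The costs are a longer answer list per drug, some extra coding, possible credit for generic answers that happen to appear in full labelling, and possibly a smaller observed difference. The concern about generic answers is the best reason to report both scores.

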This study is being conducted with patients from clinics within Northwestern Medical Healthcare (NMHC) and Access Community Health Network (ACCESS). All physicians within the practice will be informed of the study. All telephone interviews will take place in a private space at all study sites.

2. Schedule of Activities

Table 1 shows study timeline.

Visit						
Days from Initial Index Visit	1-2	3-14	15-21	21-28	29-36	90-104
Pragmatic Study Procedure						
Screening Phone Call	X					
Written Informed consent	X					
T1 In Person* Interview	X	X				
Patient sent email to complete portal		X		X		
questionnaire (expires after 2 weeks)						
If questionnaire not complete reminder			X		X	
email sent (sent two days after initial email						
to complete portal questionnaire)						
T2 Phone Interview						X

^{*}T1 interview may be completed over the phone if an in-person interview cannot be conducted.

3. Introduction

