9.1.2. Secondary Effectiveness Assessments

Medication Adherence. Medication adherence refers to a patient's medication taking behavior in terms of the extent to which he or she takes the medication as prescribed. We will assess medication adherence by 1) treatment initiation (yes or no), 2) time to fill (# of days from prescription order to patient fill), 3) subjective self-report of medication adherence behaviors (ASK-12), 4) objective assessment of proper use.

- 1) *Treatment initiation*. Patients will be asked whether they have filled their study prescription (yes or no), and whether they intend to fill it.
- 2) *Time to fill.* We will calculate the number of days between the date the medication was ordered and when the medication was actually filled, based on the patient's self-report of the date of fill stated on the medication's prescription label from the pharmacy.
- 3) ASK-12. The ASK-12 survey is a widely used and previously validated psychometric measure of adherence that covers three domains: inconvenience/forgetfulness, treatment beliefs and behavior(15). In a study among 112 adults with asthma, type II diabetes or congestive heart failure, the tool demonstrated good internal consistency reliability (Cronbach's α 0.75) and test-retest reliability (intraclass correlation 0.79); convergent validity was also demonstrated through correlations with multiple other measures (16, 17) and pharmacy claims data (15). Ask-12 scores range from 12-60, with higher scores translating to greater barriers to adherence.
- 4) Proper use. For the study medication, patients will be asked on what day they last took the medication. While most medications will be daily and the correct response would be 'yesterday' or 'today', some prescribed drugs of interest may be taken weekly or in another manner as directed by their physician. Patients will then be asked 1) How many times during the day did you take it? 2) At what hour/s of the day did you take this medicine? and 3) How much of this medicine did you take each time? A patient's proper timing (last day and # of times per day), dosing (number of pills per dose), and spacing between doses (for BID, TID medications only) will be coded as correct or incorrect. Patients will be classified as having properly used their medication if they correctly reported all components.

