10.3.3.3. Tertiary/Exploratory Analyses

Aim 3. Evaluate the fidelity of the EMC² Strategy to promote provider counseling, deliver patient Rx information, and inform providers of potential harms.

Compared to usual care, patients receiving the EMC² strategy will:

- 1) report higher rates and quality of provider Rx counseling
- 2) report higher rates of receipt of print Rx information

Appropriate bivariate analyses will be performed based on each outcome measure described below using t-tests, Wilcoxon Rank-Sum, or $\chi 2$ tests, as appropriate.

Provider Rx Counseling. We will ask patients (yes/no) whether their provider(s) (physician/nurse) counseled them on their prescribed medication. We will also ask adapted questions from the Health Literacy supplemental items of the Consumer Assessment of Health Providers Survey (CAHPS) to evaluate the extent and quality of physician verbal counseling.

Receipt of print Rx information. All patients will be asked whether they received any print Rx information at their appointment. We will further probe intervention patients to determine whether the health literate Med Guide Summary was specifically received and its perceived helpfulness. Additionally, we will also collect EHR data to determine whether the Med Guide Summary was printed with their after-visit summaries.

We will also examine completion rates of:

- 1) the EHR portal survey by patients in the intervention arm
- 2) clinic follow-up for patients identifying Rx concerns in the portal survey.

Completion of the EHR Portal Survey. Intervention patients will be asked (yes/no) whether they received the emails to visit the portal and if they completed the portal questionnaire. We will also confirm this by determining if portal questionnaire results were populated in the EHR.

Clinic follow-up for patients identifying Rx concerns. At each performance site, clinical liaisons will share with the study team what specific medication-related concerns that are self-reported by patients via the portal assessment might warrant follow-up. It is at the discretion of each clinical practice to choose how they will triage the information provided via the feedback from the EMC2 intervention, and as part of the study we will explore the frequency and nature of follow-up that occurred for various medication-related concerns by self-report and in the EHR.

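### The protocol states no closed-book step for the 3-month phone knowledge interview, although the answer key is a sheet that only EMC² patients are given

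*Combined protocol and SAP*

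**What the plan says.** - **Mode of the primary assessment.** Section 10.1 bases the sample size on medication knowledge at T2. Section 7.9.4: "The T2 interview will take place over the phone 3 months after T1". Only T1 can be in person, and the note to Table 1 relaxes even that: "T1 interview may be completed over the phone if an in-person interview cannot be conducted".
- **How the items are asked.** Section 9.1.1 describes open-ended questions on indication, risks or warnings, and side effects: "While patients are not given response options to facilitate their answer, interviewers will both document the verbatim response" and code it right or wrong.
- **How they are scored.** The same section sets the key: "Correct answers will be tailored to the available content included in the MedGuide Summary". It adds a check on coding: "A second, independent reviewer, blinded to the research interviewer's code of correct/incorrect, will rate the responses".
- **Who holds the key.** In section 7.1 the one-page Summary is an EMC² component, printed at the encounter or placed in the portal for telemedicine orders. The example MedSheet attachment has rows for purpose, warnings and side effects, which correspond to the three scored domains. For usual care, the Synopsis says that clinics give out no print material and pharmacies vary; section 7.1 calls it variable in both.
- **A label question in the interview.** Section 9.1.2 bases time to fill on the patient's "self-report of the date of fill stated on the medication's prescription label from the pharmacy". Table 4 marks fill and time to fill at both T1 and T2.

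No section asks patients to set materials aside, asks whether they consulted any, or fixes the order of the T2 items.

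**The concern.** The endpoint is meant to show what patients understand at 3 months. On a telephone call the interviewer cannot see what the patient is looking at. If some patients answer from a document, the score partly measures having that document to hand. This would matter less if both arms had the same document. Here the document that defines the correct answers is part of the intervention, so look-up is likely to favour EMC².

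The safeguards in 9.1.1 address other problems. Withholding response options prevents guessing from a list. Verbatim recording and a second rating protect against coding error. An answer read aloud from the Summary is a correct answer, and both raters would code it so. At stake is whether a positive primary result can be read as better knowledge.

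**Working it through.** **Inputs from section 10.1:** usual-care mean 55.6, SD 28.4, 150 per arm, 6 per provider, ICC 0.001 (0.01 as the alternative), 80% power, detectable difference 9.4 (9.6). Two-sided alpha of 0.05 is from section 10.3.1, and about 50 prescribers from section 7.3.

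**Step 1: the plan's own figure.** Design effect = 1 + (6 − 1) × 0.001 = 1.005. SE = 28.4 × √(2/150 × 1.005) = 3.29. A non-central t with 50 − 2 = 48 df gives a detectable difference of 9.40, and 9.61 at ICC 0.01. The stated 9.4 and 9.6 reproduce. The normal approximation gives 9.21 and 9.41.

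**Step 2: bias formula.** Assume no true effect, so that both arms would average 55.6 from memory. Let a share q of EMC² patients look up answers and average S, and let no usual-care patient do so.

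Spurious difference = q × (S − 55.6)

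**Step 3: numbers.** q, S and zero usual-care look-up are all assumptions; none is in the documents. The chance of a significant result uses the normal approximation with the SE from step 1 and the SD held at 28.4.

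| | S = 80 | S = 90 | S = 100 |
|---|---|---|---|
| Difference at q = 10% | 2.44 | 3.44 | 4.44 |
| Chance of p < 0.05 at q = 10% | 12% | 18% | 27% |
| Difference at q = 20% | 4.88 | 6.88 | 8.88 |
| Chance of p < 0.05 at q = 20% | 32% | 55% | 77% |
| q that gives 9.4 points | 39% | 27% | 21% |

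The last row is 9.4 / (S − 55.6): 9.4/24.4, 9.4/34.4 and 9.4/44.4. At S = 85 it is 9.4/29.4 = 32%.

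**Step 4: relaxing zero usual-care look-up.** If a share u of usual-care patients also look up answers and average V, the difference becomes q × (S − 55.6) − u × (V − 55.6). For example, with q = 10%, S = 90, u = 5% and V = 80 (again assumptions), it is 3.44 − 1.22 = 2.22 points. Look-up in usual care shrinks the bias; it disappears only if the two terms are equal.

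**The case against.** **The interview script is not in the documents.** The measures are still to be created, and section 12-style training detail is left to standardised interview protocols with competence checks. A put-papers-aside line may well be in them. This stands: the finding is that the protocol does not state such a step, and a reader should not infer that interviewers will permit look-up. But 9.1.1 already covers item format, scoring, second rating and resolution of disagreements, so the step belongs there.

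**The label question is common to both arms.** One might infer that it makes patients fetch the medicine and so creates the bias. The documents do not say that the label is in hand during the call, the label is not the Summary, and the question goes to everyone. It cannot by itself produce an arm difference. It is a reason to order the items sensibly, no more.

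**A one-arm reminder at T1.** One might also infer that EMC² patients alone are reminded of the sheet before the primary outcome. Section 10.3.3.3 does say "We will further probe intervention patients to determine whether the health literate Med Guide Summary was specifically received and its perceived helpfulness", but gives no time for that probe. The Table 4 rows marked at T1 cover receipt of a Med Guide and helpfulness of the intervention; they neither name the Summary nor limit themselves to one arm. The inference joins two places that the documents do not join.

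**Usual care is not empty-handed.** Patients there may have pharmacy leaflets or Medication Guides, and all participants must have internet access and a portal account (section 6.1). This stands: the EMC² advantage is relative, not absolute.

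**Verbatim responses would show reading aloud.** Sometimes, perhaps. But naming an indication or two side effects looks much the same from memory as from a page.

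**In a pragmatic trial, having a reference is itself a benefit.** That is a fair aim, but the stated endpoint is demonstrated understanding, not access to a document. Recording consultation allows both to be reported.

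**Conclusion.** The point holds as a gap in the written plan. The primary score is taken by phone, its key is a sheet given to one arm, and nothing stated prevents, records or allows for look-up. The resulting risk of bias runs mainly towards EMC², and double coding does not remove it.

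The size cannot be determined from the documents. The 3.4 points (q = 10%, S = 90) and the 21% to 32% needed to reach 9.4 points (S = 100 to 85) illustrate sensitivity; they do not estimate what will happen. A reader might take them to mean that the planned effect could plausibly be all artefact. The documents do not support that: it would need roughly a fifth to a third of EMC² patients to have the sheet to hand, on paper or in the portal, about 3 months after the visit and to read from it, with no look-up in usual care. The smaller shares matter more in practice, because a difference of a few points already raises the chance of a false positive above 5%.

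**What to change.** In section 9.1.1, for both arms at T2:

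1. Before the knowledge items, have the interviewer ask the patient to put aside papers, packaging and the portal and to answer from memory.
2. After those items, record yes/no whether any material was consulted. Report the count by arm and a sensitivity analysis of the primary outcome that uses this item, for example with the scores of patients who consulted material set to missing and imputed. Consultation arises after randomisation, so this analysis should support the primary comparison and not replace it.
3. Ask the knowledge and proper-use items before the label fill-date item, since the patient may have the package to hand for that question.

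Leave the Summary receipt and helpfulness probes where they are. Moving them to the end of T2 would make them depend on 3-month recall, and an EHR print record shows printing rather than receipt.

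The cost is a slightly longer script and one extra data item. Sample size, arms and contact schedule do not change. The step has to be in place before T2 interviews are done, because look-up that was not recorded cannot be reliably identified later.
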